#### 8.2.4 Rationale for Study Assessments

The safety and PK assessments are standard parameters for clinical studies in drug development. The efficacy assessments are widely accepted and generally recognized as reliable, accurate, and relevant to the study of patients with CF.

Spirometry: Since lung disease is the major cause of morbidity and mortality for patients with CF, CF lung disease is the desired primary target of VX-661/ivacaftor combination therapy. Spirometry (as measured by FEV1) is the most widely implemented standardized assessment to evaluate lung function. Spirometry assessments will be performed predose in all subjects according to Section 11.6.1. To meet a request from a regulatory authority, subjects <18 years of age at the Screening Visit will have additional spirometry assessments performed after dosing at the time points noted in Table 3-2.

Sweat Chloride Testing: In patients with CF, the underlying ion-transport defect in CFTR results in elevated sweat electrolyte levels. The sweat chloride test (quantitative pilocarpine iontophoresis) is the most common diagnostic tool for CF. A sweat chloride concentration of  $\geq 60$  mmol/L is considered to indicate CF, whereas  $< 40$  mmol/L is considered normal. Based on the mechanisms of action of VX-661 and ivacaftor, the sweat chloride test was included in this study as a measure of the effect of ivacaftor and VX-661 in combination with ivacaftor on CFTR activity.

CFQ-R: The CFQ-R is a frequently used CF-specific instrument that measures the health-related quality of life of patients with CF. As both ivacaftor and VX-661 in combination with ivacaftor are systemic therapies, they have the potential to improve respiratory symptoms as well as other extrapulmonary manifestations of CF. These improvements can be captured by the non-respiratory symptoms domains of the CFQ-R. Linguistically validated versions of the CFQ-R are available, thereby allowing consistent interpretation of the results in this global study. The CFQ-R will be used to capture and evaluate the impact of ivacaftor and VX-661 in combination with ivacaftor on patient report of respiratory symptoms and other aspects of health-related quality of life.

[REDACTED]

[REDACTED]

## 9 STUDY POPULATION

Eligibility will be reviewed and documented by an appropriately qualified member of the investigator's team before subjects are enrolled.

### 9.1 Inclusion Criteria

Subjects who meet all of the following inclusion criteria will be eligible:

1. Subject (or their legally appointed and authorized representative) will sign and date an informed consent form (ICF) and, where appropriate, assent form.
2. Willing and able to comply with scheduled visits, treatment plan, study restrictions, laboratory tests, contraceptive guidelines, and other study procedures.
3. Subjects (male and female) will be aged 12 years or older on the date of ICF or, where appropriate, date of assent.
4. Heterozygous for *F508del-CFTR* mutation and a second *CFTR* allele with a gating defect that is clinically demonstrated to be ivacaftor-responsive (Section 16). The results of the confirmatory genotype sample obtained at the Screening Visit must be reviewed before enrollment.
5. For subjects exposed to ivacaftor within 28 days prior to the Screening Visit, an FEV1  $\geq 40\%$  and  $\leq 90\%$  of predicted normal for age, sex, and height (equations of Hankinson et al. or Wang et al.) during screening (Section 11.6.1).

For subjects who have not been exposed to ivacaftor within 28 days prior to the Screening Visit, an FEV1  $\geq 40\%$  and  $\leq 75\%$  of predicted normal for age, sex, and height (equations of Hankinson et al. or Wang et al.) during screening (Section 11.6.1).

Spirometry measurements must meet ATS/ERS criteria for acceptability and repeatability (Section 8.1.1.1).

*Subjects must meet either inclusion criterion 6 or 7.*

6. Sweat chloride value  $\geq 60$  mmol/L from test results obtained during screening OR as documented in the subject's medical record (may be collected prior to Kalydeco use).
7. If the sweat chloride value is  $< 60$  mmol/L, there must be documented evidence of chronic sinopulmonary disease manifested by at least 1 of the following:
  - Persistent colonization/infection with typical CF pathogens, including *Staphylococcus aureus*, *Haemophilus influenzae*, and mucoid and nonmucoid *Pseudomonas aeruginosa*

- Chronic cough and sputum production
- Persistent chest radiograph abnormalities (e.g., bronchiectasis, atelectasis, infiltrates, hyperinflation)
- Nasal polyps, chronic sinusitis; radiographic or computed tomographic abnormalities of the paranasal sinuses

If it is unclear whether a subject meets this criterion, please consult with the medical monitor prior to enrollment.

8. Stable CF disease as judged by the investigator.
9. Willing to remain on a stable CF medication regimen from Week -4 through the last day of dosing (Week 8) or, if applicable, the Safety Follow-up Visit.
10. Willing to discontinue use of physician-prescribed ivacaftor (Kalydeco) from Week -4 to the last day of dosing (Week 8). Beginning Week -4, subjects will receive ivacaftor (Kalydeco) as the study drug.

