### **8.1.4 Safety Follow-up**

The Safety Follow-up Visit assessments are listed in [Table 3-2](#). There will be an outpatient Safety Follow-up Visit 28 days  $\pm$  7 days after the last dose of study drug for subjects who complete study drug dosing and for subjects who prematurely discontinue study drug dosing. If the Early Treatment Termination (ETT) Visit occurs 3 weeks or later following the last dose of study drug, then the ETT Visit will replace the Safety Follow-up Visit, and a separate Safety Follow-up Visit will not be required.

The Safety Follow-up Visit is not required for subjects who complete the Week 8 Visit and have enrolled in the extension study of VX-661 in combination with ivacaftor within 28 days after the last dose of study drug.

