### **8.1.5 Early Treatment Termination**

If the subject prematurely discontinues study treatment, an ETT Visit should be scheduled as soon as possible after the subject decides to terminate study treatment. Subjects who prematurely discontinue treatment will also be required to complete the Safety Follow-up Visit, approximately 28 ( $\pm$  7) days after their last dose of study drug. The assessments performed at the Safety Follow-up Visit are listed in [Table 3-2](#).

If the ETT Visit occurs 3 weeks or later following the last dose of study drug, then the ETT Visit will replace the Safety Follow-up Visit, and a separate Safety Follow-up Visit will not be required.

Subjects who prematurely discontinue study drug treatment during the Ivacaftor Run-in Period will not be randomized or participate in the Active Comparator Treatment Period. These subjects will complete an ETT Visit and Safety Follow-up Visit. The Safety Follow-up Visit will be their last visit in the study.

Subjects who prematurely discontinue study drug treatment during the Active Comparator Treatment Period will continue to complete all other scheduled study visits for assessments of efficacy (spirometry, sweat chloride, and CFQ-R) [REDACTED] as detailed in the Schedules of Assessments (Section 3).

If the subject withdraws from the study and also withdraws consent for disclosure of future information, no further evaluations should be performed and no additional data should be collected. Vertex may retain and continue to use any data collected before such withdrawal of consent.

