### **9.3 Study Restrictions**

#### **9.3.1 Dietary Restrictions/Prohibited Medications**

Prohibited medications and certain foods are not allowed in this study (Screening Period through Safety Follow-up Visit) while subjects are receiving study drug (Table 9-1). Both ivacaftor and VX-661 are metabolized predominantly via the hepatic enzymatic pathway utilizing CYP3A4. Therefore, the use of known inducers and inhibitors of CYP3A, which have the potential to significantly alter the exposure of VX-661 and ivacaftor, will be restricted in this study.

A nonexhaustive list of study prohibitions and cautions for food and medication will be provided in the Study Reference Manual.

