**Table 9-1 Study Restrictions**

Restricted Medication/Food	Study Period	
	Screening Period	Ivacaftor Run-in and Active Comparator Treatment Period
Certain fruits and fruit juices (Grapefruit, grapefruit juice, Seville oranges, marmalade)	None allowed within 14 days before the first dose of the study drug (Week -4)	None allowed through the Safety Follow-up Visit
Moderate and strong CYP3A inducers	None allowed within 14 days before the first dose of the study drug (Week -4)	None allowed through the Safety Follow-up Visit
Moderate and strong CYP3A inhibitors (except for ciprofloxacin)	None allowed within 14 days before the first dose of the study drug (Week -4)	None allowed through the Safety Follow-up Visit
Commercially available ivacaftor (Kalydeco)	Permitted during the Screening Period but none allowed after the first dose of the study drug (Week -4)	None allowed through the Safety Follow-up Visit
Commercially available CFTR modulators other than ivacaftor (Kalydeco)	None allowed within 30 days before the Screening Visit.	None allowed through the Safety Follow-up Visit

CYP: cytochrome P450.

Note: The use of restricted medication by subjects with medical needs will be addressed on a case-by-case basis with the medical monitor.

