**9.4 Prior and Concomitant Medications**

Information regarding all prior and concomitant medications, including the subject's CF medications, other medications, and herbal and naturopathic remedies administered from 28 days before the Screening Period through the Safety Follow-up Visit, if applicable, will be recorded in each subject's source documents. For subjects who are screened but are not subsequently enrolled into the study, details of prior medication will only be documented in the subjects' source documents.

- Subjects must remain on a stable medication (and supplement) regimen for their CF from 28 days before Week -4 through the Safety Follow-up Visit. Stable medication regimen is defined as the current medication regimen for CF that subjects have been following for at least 28 days before Week -4. Subjects must not initiate long-term treatment with new medication from 28 days before Week -4 through the Safety Follow-up Visit unless it is discussed and approved by the Vertex medical monitor. Guidelines for stable medication regimens for CF are as follows:
  - Subjects who are taking daily inhaled tobramycin or other chronically inhaled antibiotics should remain on that regimen throughout the study.
  - Subjects who are on inhaled cycling antibiotics should continue on their prior schedule. The timing of the first dose of study drug should be synchronized as closely as possible to the first day of inhaled cycling antibiotics in the cycle.

- Subjects who alternate 2 different antibiotics monthly should remain on the same schedule during the study. The timing of the first dose of study drug should be synchronized as closely as possible to the first day of 1 of the inhaled alternating antibiotics.
- Subjects may receive doses of prednisone of up to 10 mg/day (chronically) or prednisone 60 mg qd for up to 5 days without prior approval of the medical monitor.
- Information about bronchodilator use during the study will be collected and documented. Subjects who are using a bronchodilator must have their spirometry assessments performed according to the guidelines provided in [Section 11.6.1](#).
- Concomitant use of medications known to prolong the QT interval should be used with caution during the study, as the effect of VX-661 in combination with ivacaftor on the QT interval has not been evaluated in a thorough QT study. Consideration should be given to obtaining an ECG when concomitant medication known to prolong the QT interval is administered.

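### Do the differing end dates for the restriction on commercial ivacaftor call for a change to the plan?

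*Protocol*

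**What the plan says.** Four places in the protocol bear on how long a subject stays off prescribed ivacaftor.

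- **Section 9.1, criterion 10** asks that the subject be "Willing to discontinue use of physician-prescribed ivacaftor (Kalydeco) from Week -4 to the last day of dosing (Week 8". Its next sentence explains that ivacaftor is supplied as study drug from Week -4.
- **Section 9.1, criterion 9**, on the stable CF regimen, runs "through the last day of dosing (Week 8) or, if applicable, the Safety Follow-up Visit". Criterion 10 has no such addition.
- **Section 9.3.1** introduces the restrictions in general terms: "Prohibited medications and certain foods are not allowed in this study (Screening Period through Safety Follow-up Visit) while subjects are receiving study drug".
- **Table 9-1**, commercial ivacaftor row, permits use in screening, stops it at the first dose at Week -4, and for the treatment periods says "None allowed through the Safety Follow-up Visit".

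Three provisions frame these. Criterion 2 requires willingness to comply with study restrictions, which is the subject of Section 9.3. The note under Table 9-1 lets the medical monitor deal individually with subjects who have a medical need for a restricted drug. Sections 8.1.4 and 8.1.5 place the Safety Follow-up Visit 28 days (give or take 7) after the last dose and describe subjects who have no separate visit.

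**The concern.** The start of the restriction agrees everywhere it is stated for this drug, but the end does not. Criterion 10 stops at the last dosing day, which it equates with Week 8. Table 9-1 continues to the Safety Follow-up Visit. Section 9.3.1 puts both limits in one sentence. The drug is some subjects' own prescribed therapy: Section 8.2.3 expects to enrol people already taking ivacaftor as well as people who are not. Two sites reading different sections could therefore advise subjects differently once study drug ends.

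The statistical stake would lie with early discontinuers. They keep attending through Week 8, and SAP Sections 9.3 and 9.3.1.3 include their values after stopping study drug in the primary model. Whether such a subject has resumed ivacaftor affects what those values represent.

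**Working it through.** The plan states no figure on this point, so there is nothing to reproduce. The check compares the texts, then the calendar, then the analysis rules.

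**Texts side by side**

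| Place | Kind of statement | Start | End |
|---|---|---|---|
| Criterion 10 | Willingness at entry, this drug | Week -4 | Last dosing day (Week 8) |
| Table 9-1 | Prohibition, this drug | First dose, Week -4 | Safety Follow-up Visit |
| Section 9.3.1 | General lead-in, all restricted items | Screening | Both limits |

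Section 9.3.1 cannot be a precise window for ivacaftor, because its screening start contradicts the row that permits ivacaftor in screening. Criterion 10 and Table 9-1 differ in length but can both be obeyed: criterion 10 does not say that use may resume.

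**Inputs**

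- Week 8 Visit: Day 57 ± 5, so Day 52 to 62 (Protocol Table 3-2).
- Last dose for a completer: the evening before that visit (Section 10.2), nominally Day 56, range Day 51 to 61.
- Safety Follow-up Visit: last dose + 21 to + 35 days (Section 8.1.4).
- Week 8 analysis window: Day 44 to 71 (SAP Appendix D).

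**Completers who do not roll over**

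- Nominal: 56 + 21 = Day 77 and 56 + 35 = Day 91. The gap is 77 − 56 = 21 to 91 − 56 = 35 days.
- With the Week 8 window: 51 + 21 = Day 72 and 61 + 35 = Day 96.
- SAP Appendix D maps a follow-up efficacy measurement to a regular visit only up to Day 71. The earliest in-window follow-up is Day 72, so it cannot enter the Week 8 analysis.
- The interval in question opens on the day of the Week 8 Visit, which criterion 10 itself names, and otherwise lies wholly after the last efficacy assessment.

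**Early discontinuers, last dose on Day L**

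- With a separate Safety Follow-up Visit, Table 9-1 ends at L + 21 to L + 35. Criterion 10 ends at L or at about Day 56, depending on which half of its wording is used.
- For L = 14, Table 9-1 gives Day 35 to 49; for L = 50, Day 71 to 85. The order of the end dates is therefore not fixed.
- No firm bound follows, because Section 8.1.5 lets a late ETT Visit replace the Safety Follow-up Visit and sets no upper limit on its timing.
- The primary model takes in measurements after treatment discontinuation, and the public text sets no condition on concomitant ivacaftor. The same records are analysed in the same way under either reading.

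**Recording of use**

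- Footnote v (Protocol Table 3-2 and SAP Table 12-2) collects all medications through the Safety Follow-up Visit. From there to Week 8 it names only certain antibiotics.
- For L = 14 that stretch is 57 − 49 = 8 to 57 − 35 = 22 days nominally. With the Week 8 window it is 52 − 49 = 3 to 62 − 35 = 27 days. It can arise when L + 21 ≤ 62, that is L ≤ 41.
- A drug started in that stretch would fall after the treatment-emergent period (SAP Section 8.3: the earlier of the Safety Follow-up Visit and 28 days after the last dose). SAP Section 9.2.4 would only list it as a post-treatment medication.

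**The case for a change.** The best case for a change is that nothing in the text breaks the tie. Criterion 9 names the Safety Follow-up Visit and its neighbour does not, so the omission can look deliberate. Section 9.4 does not settle it either: "Stable medication regimen is defined as the current medication regimen for CF that subjects have been following for at least 28 days before" Week -4 can describe prescribed ivacaftor in a prior user, while "Subjects must not initiate long-term treatment with new medication from 28 days before Week -4 through the Safety Follow-up Visit" leaves open whether resuming it counts as new. Some subjects never reach the end point that Table 9-1 names. After a late ETT Visit, "then the ETT Visit will replace the Safety Follow-up Visit, and a separate Safety Follow-up Visit will not be required"; and for others, "The Safety Follow-up Visit is not required for subjects who complete the Week 8 Visit and have enrolled in the extension study". Early discontinuers' values do enter the primary model, and a fuller record of ivacaftor use would help a reader interpret them.

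The wording mismatch stands, as does the absence of a stated end for subjects without a separate follow-up visit. The Section 9.4 argument is weak, because Table 9-1 names this drug and a general clause on stable regimens hardly reopens the point. That sites would in fact give different advice is conjecture: Section 9.3.1 refers to a Study Reference Manual that is not available here, and the table's note gives sites a route to the medical monitor. The recording point is a separate matter. It depends on Section 11.6.4.1.1, which footnote v cites and the public text does not contain. Protocol Table 3-2 also marks concomitant medications at Week 8, and no analysis in the public SAP would use the extra record.

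**Conclusion.** The inconsistency is genuine but clerical. For completers who do not roll over it amounts to 21 to 35 days, and their primary data are unaffected. For early discontinuers no effect size can be derived: the documents do not say how many will have access to prescribed ivacaftor or resume it. The estimand, model, multiplicity procedure and stated power are the same whichever end date is meant, so a sponsor following the plan as written reaches the same results.

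This rests on visits keeping to their windows, on reading criterion 10 as a statement of willingness alongside criterion 2, and on the public text alone. Criterion 10, Section 9.3.1 and Table 9-1 remain for the sponsor to reconcile as a matter of wording. The choice of end date is a clinical one, and none is proposed here.

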## 9.2 Exclusion Criteria

Subjects who meet any of the following exclusion criteria will **not** be eligible.

1. History of any comorbidity that, in the opinion of the investigator, might confound the results of the study or pose an additional risk in administering study drug to the subject. For example, a
  - history of cirrhosis with portal hypertension and/or
  - history of risk factors for Torsades de Pointes (e.g., familial long QT syndrome, hypokalemia, heart failure, left ventricular hypertrophy, bradycardia, myocardial infarction, cardiomyopathy, history of arrhythmia [ventricular and atrial fibrillation], obesity, acute neurologic events [subarachnoid hemorrhage, intracranial hemorrhage, cerebrovascular accident, or intracranial trauma], and autonomic neuropathy).
2. Any of the following abnormal laboratory values at the Screening Visit:
  - Hemoglobin <10 g/dL
  - Abnormal liver function defined as any 2 or more of the following:
    - $\geq 3 \times$  upper limit of normal (ULN) aspartate aminotransferase (AST),
    - $\geq 3 \times$  ULN alanine aminotransferase (ALT),
    - $\geq 3 \times$  ULN gamma-glutamyl transpeptidase (GGT),
    - $\geq 3 \times$  ULN alkaline phosphatase, or
    - $\geq 2 \times$  ULN total bilirubin
  - Abnormal liver function defined as any increase of  $\geq 5 \times$  ULN AST or ALT
  - Abnormal renal function defined as glomerular filtration rate  $\leq 50$  mL/min/1.73 m^2 (calculated by the Modification of Diet in Renal Disease Study Equation) for

subjects  $\geq 18$  years of age and  $\leq 45$  mL/min/1.73 m^2 (calculated by the Counahan-Barratt equation) for subjects aged 12 to 17 years (inclusive).

3. An acute upper or lower respiratory infection, pulmonary exacerbation, or changes in therapy (including antibiotics) for pulmonary disease within 4 weeks before Week -4 (first dose of study drug for the Ivacaftor Run-in Period).
4. A 12-lead ECG demonstrating QTc >450 msec at the Screening Visit. If QTc exceeds 450 msec for the screening ECG, the ECG should be repeated 2 more times during the Screening Period, and the average of the 3 QTc values should be used to determine the subject's eligibility.
5. History of solid organ or hematological transplantation.
6. History or evidence of cataract, lens opacity, Y-suture, or lamellar rings determined to be clinically significant by the ophthalmologist during the ophthalmologic examination during the Screening Period. The ophthalmologic examination does not need to be repeated if there is documentation of an examination meeting protocol criteria that was conducted within 3 months before the Screening Period or if there is documentation of bilateral lens removal ([Section 11.7.8](#)).
7. History of alcohol or drug abuse, as deemed by the investigator, in the past year, including but not limited to cannabis, cocaine, and opiates
8. Ongoing or prior participation in an investigational study drug (including studies investigating lumacaftor [VX-809] or VX-661) within 30 days of the Screening Visit.
  - A washout period of 5 terminal half-lives of the previous investigational study drug or 30 days, whichever is longer, must elapse before the Screening Visit. The duration of the elapsed time may be longer if required by local regulations.
  - Subjects enrolled in open-label extension studies of ivacaftor are not excluded from enrollment.
  - Ongoing participation in a noninterventional study (including observational studies and studies requiring assessments without administration of study drug) is permitted.
9. Use of restricted medications or foods within the specified window before the first dose of study drug as defined in [Table 9-1](#).
10. Pregnant and nursing females (females of childbearing potential must have a negative pregnancy test at Screening and Week -4 Visits).
11. The subject or a close relative of the subject is the investigator or a subinvestigator, research assistant, pharmacist, study coordinator, or other staff directly involved with the conduct of the study. An adult (aged 18 years or older) who is a relative of a study staff member may be enrolled in the study provided that
  - the adult lives independently of and does not reside with the study staff member.
  - the adult participates in the study at a site other than the site at which the family member is employed.

12. Colonization with organisms associated with a more rapid decline in pulmonary status (e.g., *Burkholderia cenocepacia*, *Burkholderia dolosa*, and *Mycobacterium abscessus*). For subjects who have had a history of a positive culture in the past, the investigator could be guided by the following suggested criteria for a subject to be considered free of colonization:

- The subject should have had 2 respiratory tract cultures negative for these organisms within the past 12 months, with no subsequent positive cultures.
- These 2 respiratory tract cultures should have been separated by at least 3 months.
- One of these 2 respiratory tract cultures should have been obtained within the past 6 months.

